1. PURPOSE OF THE STUDY

a. Brief Summary

The overarching goal of this research program is to elucidate causal and directional neural network-level abnormalities in depression, and how they are modulated by an individually-tailored, circuit-directed intervention.

b. Objectives

To examine the impact of antidepressant rTMS on causal network abnormalities in depression, and the relationship between baseline networks deficits and clinical outcome.

c. Rationale for Research in Humans

This is a study of Major Depressive Disorder in humans.

2. STUDY PROCEDURES

a. Procedures

All eligible subjects will undergo structured diagnostic interviews, including a MDD-specific assessment at Stanford shortly after recruitment. Subjects will then have a pre-treatment baseline MRI session (structural, resting), a concurrent fMRI/TMS scan session and a concurrent EEG/TMS session within two weeks at one of the Stanford scan sites. Preparation for physiological measurements will take 30-40 minutes including calibration time. These initial assessments provide a baseline for comparing pre- to post-treatment brain changes in patients. In the case of the baseline assessments, TMS is a probe for testing brain circuitry and as such, actual TMS must be used. All participants, whether randomized to active or sham, complete the TMS baseline assessments in order to provide baseline brain activation profiles.

After determining study eligibility, participants will wear an EEG cap which is like a swimming cap with Ag/AgCl electrodes which will be filled with gels through syringe. The Ag/AgCl electrodes for EOG.

Subjects will then be randomized to receive 4 weeks daily rTMS vs. sham (placebo) treatment sessions (total 20). For participants who receive sham (placebo) treatment for the first 4 weeks, they are offered 4 weeks of open-label active treatment. For participants who receive active

treatment during the first 4 weeks of treatment, they are not offered another 4 weeks of treatment.

Finally, another fMRI/TMS scan and EEG/TMS session will be scheduled within one week post rTMS treatment. Depression and anxiety will be evaluated using MDD and anxiety specific assessment pre and post- rTMS/sham treatment and after the 10th and 20th (and 30th and 40th for open-label patients) treatment session during rTMS/sham.

Patients who drop out of treatment will be encouraged to return for clinical and imaging assessments. Participants who continue onto the open-label treatment will also come in for another fMRI/TMS scan and EEG/TMS session within 1 week after their second 4 weeks of treatment.

b. Procedure Risks

The experiment will terminate at the conclusion of the TMS stimulation and fMRI data acquisition or at any point that a subject requests to terminate the experiment. In addition, if the subject does not respond to questioning about their well-being during the experiment, the experiment will be terminated. If the experiment must be terminated for any reason that requires acute medical intervention, EMS will be immediately notified and directed to the 3T scanner location by the experimenters.

MRI/fMRI

Some of the RF imaging coils, imaging software and devices being used in a scan are not approved by the FDA but are similar to counterparts that have been approved by the FDA. There is a small risk of heating from the cables associated with these devices.

The investigational devices used in scanning at the Lucas Center and CNI, including EEG/Physio/Eye-tracker devices, pose a non-significant risk to subjects in line with the criteria for exception from an IDE, and routinely used by many other experimenters at Stanford. There have been no serious adverse events incurred during scanning at the Lucas Center or CNI.

BrainsightTM

BrainsightTM is a stereotactic image guidance system that facilitates the positioning of TMS coils over a subject's brain. It can display the stimulation targets (derived from MRI / fMRI images) on anatomical MR images, providing an interactive navigational guide for coil positioning. It has virtually no risks except for maybe minimal fatigue from holding the head still for a few minutes.

TMS

The TMS device to be used is the MagVenture X100 with MRI-compatible coil. The TMS devices are non-significant risk devices, in line with the criteria for exception from an IDE. The principal components of the system are "figure-8" style coil made of insulated copper bus bar and four capacitor-containing "booster modules". The flow of electricity from the booster modules to the coil is regulated by a control module and a laptop computer. When a pulse of electricity flows through the coil, a magnetic field pulse is generated in accordance with Faraday's law. This magnetic pulse, in turn causes nearby neurons to discharge in a physiological variant of the Hall Effect. No electric current is ever passed between the machine and the patient. Currently, this TMS machine has FDA approval for peripheral nerve stimulation only.

The TMS devices are also non-significant risk devices, in line with the criteria for exception from an IDE. Patients are generally able to drive home or return to work immediately after an rTMS session. The most common side effect of TMS (approx 25% of patients) is a mild headache, which usually responds to the over-the-counter medications such as ibuprofen. However, no difference in headache frequency between TMS and sham treatment was reported in the recent large trials (O'Reardon et al., 2007; George et al., 2010). The rTMS can cause some scalp pain at the application site, which is usually worse during the first few sessions and then largely disappears, although a few patients drop out of studies because of this discomfort (George and Post 2011). There is also a very small risk of toothache from TMS.

Studies suggest that the loud clicking noise produced by the TMS discharge may exceed 140 dB of sound pressure level, and can cause hearing loss (Rossi et al., 2009). A small subset of adults experienced transient increase in auditory thresholds post TMS. Permanent hearing loss was observed in a single individual who did not wear hearing protection. Although the majority of studies reported no change in hearing after TMS when hearing protection was used. A recent review showed no change in auditory threshold after 6-12 weeks of rTMS exposure (n=325) (Janicak et al., 2008). In our study, we require that all subjects and operators wear approved hearing protection (earplugs) during all TMS sessions as recommended by TMS safety guideline (Rossi et al., 2009).

Although rTMS are generally safe and well tolerated without enduring side effects, total 16 cases of accidental seizures induced with TMS were reported, with a sample size of several thousand patients and healthy volunteers exposed to TMS. The risk is estimated to be probably less than 0.5%. (George and Post 2011). The majority of cases reported were in healthy volunteers who received TMS to the motor cortex (the most epileptogenic region of the cortex) and the stimulation parameters were outside of the safety guideline now widely adopted (Wassermann 1998). Among the nine new cases reported after the publication of 1998 safety guideline, three of them (one case with TMS parameters outside safety guidelines) were considered to be likely non-epileptic, e.g. syncope, pseudoseizure with normal EEG; five of them (3 cases with TMS parameters outside safety guidelines) occurred in patients taking pro-epileptogenic medication (n=4) or following sleep-deprivation (n=1); one seizure case was associated with theta burst stimulation (TBS) (Rossi et al., 2009). Of note, TBS is not included in our study.

All of the seizures were self-limited, occurred during TMS administration when the subjects were sitting down and near an investigator, no medications or other interventions were required. Additionally, no recurrences were reported.

No enduring impairment of neurocognitive functioning in TMS patients has been reported. (George and Post, 2011).

Neuronetics, a TMS device manufacturer, sponsored one of the largest single studies of TMS (used for the treatment of depression) involving 155 active TMS subjects. There were no reports of any serious adverse events, including seizure (O'Reardon et al., 2007). A recent NIH sponsored, industry independent, randomized, active sham-controlled trail in depression found only minimal adverse effects reported by participants (n=190) that did not differ between active rTMS treatment group vs. sham (George et al, 2010).

In summary, TMS (single-pulse TMS and rTMS) are generally safe and well-tolerated, however, seizures remain a rare but significant adverse event. In our study, all stimulation parameters are determined to comply with the safety guidelines for TMS (Wasserman, 1998; Rossi et al., 2009). In the event of adverse effects related to MRI/fMRI scanning and TMS, safety coordinators and medical staff at the Lucas Center and CNI will be on-site for consultation and assistance. The Stanford University Hospital Emergency Room is less than a 5-minute walk from the Lucas Center or 10 minutes from CNI. Finally, [name], the PI of this study, is a licensed physician and will oversee all research clinicians and monitor any adverse situations that might arise during the course of 20-40 sessions of rTMS at the psychiatry outpatient clinic, as well as the MRI/fMRI scans.

c. Use of Deception in the Study

Not applicable

d. Use of Audio and Video Recordings

Not applicable

e. Alternative Procedures or Courses of Treatment

The alternative to participation is not participation.

f. Will it be possible to continue the more (most) appropriate therapy for the participant(s) after the conclusion of the study?

This will not be possible. Daily rTMS treatment for MDD is intended to be a brief course of intervention. We do offer open-label rTMS to patients in sham group.

g. Study Endpoint(s)

The endpoint of the study is fMRI/TMS scans post rTMS treatment. Although this study involves rTMS and sham treatment, our goal is to explore the brain circuit involved in clinical improvement in response to focal, non-invasive brain stimulation with rTMS, not the efficacy of rTMS vs sham. In addition, we do offer open-label rTMS to the sham group.

Primary Outcome Measure:

Clinician administered HAM-D

The Hamilton Depression Rating Scale (HAM-D) is a 24-item clinician-administered assessment utilized as a way of determining a patient's level of depression before, during, and after treatment. It takes approximately 15-20 minutes to complete the interview and score the results.

Exploratory Outcome Measures:

fMRI/TMS assessed neural network connectivity [Time Frame: Up to 3 months.] From pre- to post-treatment, improvement will be based on enhanced functional connectivity.

Implicit emotion regulation [Time Frame: Up to 3 months]

Implicit emotion regulation assessed through emotion conflict task performed during functional imaging. Performance based on reaction time and recruitment of emotion regulation regions during the task.

fMRI-assessed resting connectivity [Time Frame: Up to 3 months.] From pre- to post-treatment of patients with high-frequency repetitive TMS (rTMS) improvement shall be measured by normalization of baseline network-level deficits.

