10. STATISTICAL ANALYSIS PLAN

For the depression group, t-tests and ANOVAs will be performed to examine the effect of rTMS treatment, compared to sham, on network activity by comparing the follow-up TMS/fMRI scan to the initial scan between those two groups (N=20/group) – doing so will determine the network changes associated with real rTMS, since we have a convincing sham control arm. Additionally, we will use multiple regressions to examine the relationship between network-level activity change and clinical response to rTMS treatment in the real treatment group. Baseline TMS/fMRI moderators of treatment response will be examined using multiple regressions in the real treatment group.

Power calculation: Not Applicable.

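### Section 2g contradicts itself on what is primary (HAM-D or the TMS/fMRI measure), and Section 10 gives no between-arm estimate of HAM-D, the named primary outcome

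*Combined protocol and SAP*

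**What the plan says.** Section 2g makes two statements about purpose and then ranks the outcomes.

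- On purpose: "The endpoint of the study is fMRI/TMS scans post rTMS treatment". The next sentence says that the interest is in the brain circuit behind clinical improvement, "not the efficacy of rTMS vs sham".
- On ranking, the primary outcome measure is "Clinician administered HAM-D", a 24-item scale said to capture the "level of depression before, during, and after treatment". No time frame is attached. Three imaging or task measures follow as exploratory, the first being "fMRI/TMS assessed neural network connectivity [Time Frame: Up to 3 months". The other two carry the same time frame.

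Section 10, which is the whole analysis plan, has three analyses. The first is between arms, with 20 per group: "t-tests and ANOVAs will be performed to examine the effect of rTMS treatment, compared to sham, on network activity". The second regresses clinical response on network change, and the third examines baseline moderators of treatment response. Both of these are confined to the active arm. HAM-D is not named in Section 10.

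Section 1b gives two objectives: the effect of rTMS on network abnormalities, and the relation of baseline network deficits to clinical outcome. Section 2a schedules a depression assessment in both arms before and after treatment and after sessions 10 and 20. Sham participants are then offered open-label active treatment.

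**The concern.** A primary outcome should have a planned analysis, and in a randomised trial that analysis would normally compare the arms. Here the outcome labelled primary has no such comparison, while the only comparison of the arms is on a measure that appears to belong to the exploratory list. The purpose statements in 2g point to the scan and the ranking in 2g points to HAM-D, so a reader cannot tell from the document which result the trial stands on.

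Two things are at stake. First, the randomised contrast on the named primary outcome would never be estimated, although the schedule appears to collect the data for it. Second, the document leaves room to decide late which result is primary, which HAM-D visit is used, and whether it enters as a final score, a change or a responder status.

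**Working it through.** The plan's own figure first: 20 per group × 2 arms = 40, which agrees with the planned enrolment in Section 5a. Section 10 declares a power calculation not applicable, so there is no power, alpha, SD or effect size to reproduce. The check is therefore mainly a comparison of sections.

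**What each section treats as central**

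| Section | HAM-D or clinical outcome | TMS/fMRI network measure |
|---|---|---|
| 1b, objectives | related to baseline network deficits | effect of rTMS on networks |
| 2g, purpose sentences | rTMS-versus-sham efficacy disclaimed | post-treatment scan is the endpoint |
| 2g, ranking | primary, no time frame | exploratory, up to 3 months |
| 10, between arms | none | the only randomised comparison |
| 10, active arm only | undefined response term in two regressions | predictor in both |

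Only the ranking row puts HAM-D first. The other rows agree with one another.

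**Count of analyses.** Section 10 has three. One compares the arms, and its outcome is network activity. Two involve a clinical outcome, and they use 20 of the 40 planned participants. Between-arm HAM-D estimates: 0 of 3.

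**Is HAM-D used at all?** Probably. It is the only depression scale named, so the response terms in Section 10 most likely rest on it. But neither term is defined, and no visit is given.

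**Is the Section 10 measure the exploratory one in 2g?** Section 10 refers to network activity and 2g to network connectivity. Both probably come from the same TMS/fMRI data, but the terms differ and the document does not equate them.

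**How many HAM-D time points are open?** Within the randomised phase, Section 2a gives assessments after session 10, after session 20 and post-treatment. It does not say whether the last two are the same visit, so there are two or three candidates. Section 5j also mentions a 6-month visit whose assessments are not described. Time frames are given for 3 of 3 exploratory measures and not for the primary.

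**Precision of the missing comparison (context only).** Assume two-sided alpha 0.05 and no dropout; the documents give neither.

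- Unadjusted 95% half-width in SD units = t(0.975, 2n − 2) × √(2/n). With n = 20: 2.024 × √(2/20) = 2.024 × 0.316 = 0.640.
- With baseline adjustment = t(0.975, 2n − 3) × √(2/n) × √(1 − r²). With n = 20 and assumed baseline–outcome correlations r of 0.3, 0.5 and 0.7: 0.611, 0.555 and 0.458.

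The finding does not depend on these figures. They show only what the added analysis could deliver.

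**The case against.** The strongest reply is that this is a mechanistic study and says so. Section 2g disclaims efficacy, Section 1b asks about networks, and Section 10 answers both objectives: it compares the arms on networks and relates networks to clinical response. On that view the absence of a HAM-D comparison is deliberate.

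Much of this stands. A reader might infer that Section 10 is the faulty section because it inverts the 2g ranking. The documents do not support that: Section 10 fits the stated aims, and the outlier is the ranking in 2g. Nor do they support the inference that the sponsor promised an efficacy comparison and then dropped it. But the reply explains the omission without removing the contradiction. If the circuit measure is what matters, it should not be listed as exploratory under a HAM-D primary.

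A second reply is that endpoint may mean only the last procedure. Even so, the ranking still conflicts with the stated goal and with the only randomised analysis.

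A third is that HAM-D timing is given, since the scale is said to be used before, during and after treatment. That describes how the scale is used. It does not select an analysis visit.

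**Conclusion.** The point holds as a contradiction over what is primary, with a direct consequence: followed as written, the plan yields no randomised estimate of its named primary outcome (0 of 3 analyses), and HAM-D has neither an analysis time point nor a metric. It should be corrected before analysis.

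This rests on the text of Sections 1b, 2a, 2g and 10, and on two probable readings: that the response terms in Section 10 refer to HAM-D, and that network activity in Section 10 comes from the same data as connectivity in 2g. If the first reading is wrong, HAM-D has no planned analysis at all. If the second is wrong, the only randomised comparison is on a measure that 2g does not list.

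A reader might infer that the primary result and the HAM-D metric will be picked after the data are seen. The documents do not say when these choices are made, so they support only that this could happen. What the active-arm regressions can show without sham data is a separate question and forms no part of this finding.

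**What to change.** **Preferred, in line with Sections 1b and 10 and the purpose sentences of 2g.** In 2g, make one pre-specified TMS/fMRI network measure the primary outcome, and use the same term for it in Section 10. Compare it between arms as randomised at the post-treatment scan, with its baseline value as covariate. Label the other imaging tests exploratory. Make HAM-D secondary and add to Section 10:

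> HAM-D total after session 20, before any open-label treatment, will be compared between arms as randomised by ANCOVA with baseline HAM-D as covariate. The adjusted mean difference and 95% confidence interval will be reported. Participants who stop treatment and return for assessment will be included, and the number missing in each arm will be reported.

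**Alternative, if HAM-D is meant to stay primary.** Make the same ANCOVA the primary analysis and revise the endpoint and efficacy sentences in 2g to agree with it.

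**In both cases:**

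- give HAM-D a time frame in 2g;
- state in 2a that HAM-D is the depression scale used, and whether the post-treatment assessment is the one after session 20;
- define clinical response and treatment response in Section 10 as HAM-D change from baseline to after session 20.

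**Cost.** These are text edits to Sections 2a, 2g and 10, which Section 6 requires to go to the DSMB. Section 2a already schedules a depression assessment after session 20 in both arms, and it already encourages those who drop out to return. If the scale now given after session 20 is not HAM-D, one interview of 15 to 20 minutes is added. Under the preferred option the other imaging tests lose any confirmatory standing. Under either option the HAM-D estimate will be imprecise at 20 per arm, so a null result would not show absence of effect.

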3. BACKGROUND

a. Past Experimental and/or Clinical Findings

Depression is a highly prevalent and serious mental illness, has a lifetime prevalence of 16% (Kessler RC et al., 2003), and accounts for more global disability than any other illness (WHO, 2008). Studies such as STAR*D have illustrated the poor success rates of even the best-calibrated treatments. In fact, only 43% of STAR*D patients were able to achieve sustained recovery during the study period (Nelson, 2006). At the heart of this problem is the lack of a causal, mechanistic, neurobiological understanding of the pathophysiology of depression. Having such an understanding would allow the development of novel, neural network-targeting treatments.

We conducted resting-state functional connectivity (FC) analyses in a sample of 39 medicationfree depressed subjects and 38 healthy controls, seeding the FC analyses with regularly-placed spheres throughout the entire PFC. We analyzed the groupwise difference at each of these seeds, measured as the number of suprathreshold voxels at p<0.05, the regions of greatest abnormality are in the ECN, and in particular its DLPFC node. As the patient sample analyzed here is reflective of the sample to be recruited for the proposed study, these data lend further support to targeting the pMFG with TMS/fMRI and conceptualization of network-level abnormalities in depression within the context of ECN-DMN interactions.

To test for causal and directional interactions between the ECN and DMN, we conducted concurrent TMS/fMRI in 11 healthy subjects, targeting the pMFG (ECN) and compared it to targeting a more anterior prefrontal region (aMFG), which is part of a cingulo-insular emotional salience network. Stimulation of the pMFG resulted, as predicted by correlational neuroimaging studies, in deactivation of regions within the DMN, most strikingly in the VMPFC. This effect was not seen after stimulation of the aMFG, where activation in the dorsal cingulate and insula was more evident, demonstrating site- and network-specific effects of stimulation. Interestingly, the individual functional connectivity-localized pMFG site was 5.1cm [SD 0.48] anterior to the primary motor cortex, thus consistent with localization using the "5cm rule," but now framed in the conceptual context of the ECN/DMN. These data demonstrate, for the first time, a causal, inhibitory relationship between the ECN and DMN, and makes possible a novel translation to depressed patients.

b. Findings from Past Animal Experiments

There is some animal work on the neural effects of TMS, though this has generally been limited to effects at the site of stimulation. These data show that TMS stimulation leads to coupled neural and hemodynamic changes at the site of stimulation that varies with stimulation parameters (Allen et al., 2007). These results support the use of blood flowmeasuring methodologies, such as fMRI, in detecting the neurophysiological effects of TMS stimulation in the human brain. No data, however, has been reported on use of TMS in the fMRI environment with animals.

4. **DEVICES USED IN THE STUDY**

Investigational Devices (Including Commercial Devices Used Off-Label) a.

Investigational Device 1	
Name:	RF Antenna Head Coil
Description:	Part of MRI head coil (custom)
Significant Risk? (Y/N)	No
Rationale for Non-Significant Risk	This device is a required accessory to the MRI machine that is involved in detecting the MRI signal in the brain. It is a custom-built version of a standard clinical coil
Investigational Device 2	
Name:	MagPro X-100
Description:	Magventure MagPro X100- TMS stimulator
Significant Risk? (Y/N)	No
Rationale for Non-Significant Risk	It is an FDA-approved for peripheral nervous system stimulation, not CNS use, however, there is an extensive experience of TMS devices being used inside and outside of the magnet, which confirms its NSR. No modification has been made to this device for our study.
Investigational Device 3	
Name:	TMS coil
Description:	Coil Cool-B65 A/P and Electrode Cable for Cool-B65
Significant Risk? (Y/N)	No
Rationale for Non-Significant Risk	These devices are required standard accessories to the TMS machine (MagPro X100) that are involved in generating magnetic pulses.
Investigational Device 4	
Name:	BrainsightTM
Description:	A stereotactic image guidance system facilitates the positioning of TMS coils over a subject's brain.
Significant Risk? (Y/N)	No
Rationale for Non-Significant Risk	A stereotactic image guidance system facilitates the positioning of TMS coils over a subject's brain. This procedure has virtually no risks except maybe minimal fatigue for subjects from holding the head still while wearing a swimming cap for a few minutes.
Investigational Device 5	
Name:	Sigma MR750 3T scanner
Description:	3.0 Tesla Magnetic Resonance Imaging device. Used to acquire functional and anatomical brain images.
Significant Risk? (Y/N)	No
Rationale for Non-Significant Risk	As specified

5. **PARTICIPANT POPULATION**

Planned Enrollment a.

40 subjects

Age, Gender, and Ethnic Background b.

Age Range: 18-50 years old Gender: Males and Females Ethnic Background: Any race or ethnic origin

_____ Vulnerable Populations c.

Not applicable

d. Rationale for Exclusion of Certain Populations

We will include women and minorities. We will not include children as TMS work has primarily been done in adults, and therefore safety studies have not been comparably carried out in children.

e. Healthy Volunteers

No healthy volunteers are included in this study.

f. Recruitment Details

Participants will be recruited through advertisements in print and online media/websites such as craigslist.com, researchmatch.org, wesearchtogether.org, Stanford Report, and Google ads, placement of posters in public locations, targeting the entire San Francisco Bay Area. Participants will also be recruited through various clinics in Palo Alto, including Stanford Hospital and Clinics. We will provide fliers and a questionnaire at community events. In collaboration with other research teams, we will also collect interest cards from current research subjects who are interested in learning more about this study. Subjects will respond to the ads either by replying to the email posted in the ads or by calling the phone number listed. Subjects may also fill out the online interest card by visiting our website. Subjects can book their own appointments via checkappointments.com.

g. Eligibility Criteria [from CLINICAL TRIALS.GOV]

Inclusion Criteria:

Men and women, ages 18 to 50 Depression assessed through phone screen Must comprehend English well to ensure adequate comprehension of the fMRI and TMS instructions, and of clinical scales Has failed >1 previous adequate antidepressant medication trials Right-handed No current or history of neurological disorders No seizure disorder or risk of seizures

Exclusion Criteria:

Any contraindication to being scanned in the 3T scanners at the Lucas Center or CNI such as having a pacemaker or implanted device that has not been cleared for scanning at the Lucas Center or CNI

Any unstable medical condition, any significant CNS neurological condition such as stroke, seizure, tumor, hemorrhage, multiple sclerosis, etc

Current rTMS treatment or prior treatment failure with rTMS

Current electroconvulsive therapy (ECT) or prior treatment failure with ECT Currently pregnant or breastfeeding

h. Screening Procedures

Prospective participants will be known to meet as many of the inclusion/exclusion criteria as possible. Prospective participants will attend an in-clinic screening, where the project will be

explained and they will be invited to join the study by signing the informed consent. No one is considered to be a study participant until they attend the in-clinic screening and sign the consent form. After obtaining informed consent, screening will occur over a period not to exceed 3 weeks. Demographics and general medical history will be obtained including psychiatric history. A General physical and neurological exam will be performed including vital sign measurement, if applicable. A review of pre-study medications for up to 30 days prior to screening will occur. All eligible subjects will undergo structured diagnostic interviews, and clinical assessments. Although medication-free patients are ideal for our study due to minimal interference with TMS and fMRI, given the widespread use of antidepressants and benzodiazepines in this patient population, we are more likely to encounter patients who are already on antidepressants and/or benzodiazepines during screen phase, we will adjust, if clinically appropriate, some concomitant medications to make our recruitment less challenging, at the same time, without introducing significant confounding factor. Participants may be asked to complete a breathilizer and/or drug screen prior to sessions.

i. Participation in Multiple Protocols

We will ask the potential subjects if they are participating in any other protocols. They will be instructed not to participate in any other protocols during their involvement with our study without first getting prior authorization from both our research team and that of the other study. Overlapping participation will be handled on a case-by-case basis.

j. Payments to Participants

Participants will be offered \$200 to complete the entire study.

-If found ineligible due to too high of a motor threshold prior to completion of Scan 2, participant will be paid for partial completion of the study in the amount of \$75.

-Participants will be paid another \$100 upon completion of the 6-month follow-up visit. -If a participant is found to be eligible for the open-label portion of the study, he/she will be paid an additional \$100 for completing that portion along with the accompanying assessment and TMS/fMRI scan.

No monetary payment will be offered for participation in TMS or sham treatment part of the study.

k. Costs to Participants

No costs to the subject will arise as a result of participation in this study, other than cost of their own transportation to and from the medical center, and the time involved.

I. Planned Duration of the Study

Five years

